1.1 General information

A total of 90 stroke hemiplegic rehabilitation patients who were hospitalized in the Rehabilitation Department of Qianfoshan Hospital in Shandong Province from January 2022 to January 2023 were selected, meeting the diagnostic criteria for cerebral infarction and cerebral hemorrhage in the 2007 edition of the Chinese Guidelines for the Prevention and Treatment of Cerebrovascular Diseases, and confirmed by cranial CT or MR examination; All of them are first-time onset, with a course of \leq 1 month, and the lower limb of the hemiplegic side is classified as stage III or above. All participants signed an informed consent form. All patients have stable vital signs, stable condition, cooperative examination, no severe cognitive, visual, hearing impairment, no sensory aphasia, no orthopedic diseases, no lower limb muscle pain, no history of congenital diseases or other brain diseases, no history of organic or functional mental illness. Divide patients into a control group and a treatment group using a random number table method. There are 30 cases in the control group, 30 cases in the intelligent isokinetic treatment group, and 30 cases in the traditional isokinetic treatment group.

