1.2 Method

Both the control group and the two treatment groups received conventional rehabilitation therapy such as exercise therapy (once a day,

40 minutes a time, 5 times a week), occupational therapy (once a day, 30 minutes a time, 5 times a week), low-frequency electricity (once a day, 20 minutes a time, 5 times a week), acupuncture and moxibustion therapy (once a day, 20 minutes a time, 5 times a week), which complied with the recommendations on rehabilitation treatment in the 2017 edition of the Guidelines for Early Rehabilitation Treatment of Stroke in China; Intelligent isokinetic therapy adds isokinetic muscle strength training to the lower limb flexion and extension muscles of hemiplegia in the above treatments. The intelligent portable isokinetic tester of this project team was used for isokinetic training of the affected knee flexor and extensor muscles. The patient's seat backrest was adjusted to 85° , and the waist and shoulder cross straps were fixed. The proximal thighs of the test subjects were fixed with nylon buckles, the lateral condyle of the femur was the axis, and the length of the arm was 12 on the scale. The distal ankle of the lower leg was fixed above the ankle. Before training, passive joint movements were performed on the knee and ankle joints to avoid joint damage, And conduct three low resistance warm-up exercises. Choose $60^{\circ}/s$, $90^{\circ}/s$, and $120^{\circ}/s$ angular velocity isokinetic training based on the patient's specific situation. Train 10 times for each angular velocity, with 15 seconds of rest between each cycle, and 2 minutes of rest between each cycle. Train for 4 cycles according to the patient's tolerance, with an appropriate amount of training to cause

moderate muscle fatigue and no fatigue on the second day (a total of 25 minutes per training session). Train each muscle group once a day, 5 days a week, for a total of 3 weeks. The control group received 110 minutes of daily training, while the observation group received 135 minutes of daily training. Traditional isokinetic therapy has the same treatment parameters as the intelligent isokinetic group in this project group.

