1.3 Evaluation method

Before and after treatment, a dedicated person is assigned to assess whether the patient is in the control group or treatment group, which is a third-party blind assessment. Evaluate lower limb motor function using the Fugl Meyer method (total lower limb motor score 34 points, total balance score 14 points). Muscle strength, muscle tone examination, motor function, and self-care ability scores. And record the peak torque (PT) at an angular velocity of $60^{\circ}/s$. The reason for choosing this angle is because most of our subjects find it difficult to produce faster movements. PT refers to the maximum torque output generated by muscle contraction, representing the maximum muscle force generated by muscle contraction, in $N \cdot m$. In isokinetic muscle strength testing, the PT value has high accuracy and repeatability, and is considered the golden indicator of isokinetic muscle strength testing. It has high repeatability, and the peak torque measurement of knee joint flexion and extension is particularly stable. At the same time, a satisfaction questionnaire survey

was conducted on the use of different isokinetic methods, quantifying the characteristics of the two types of isokinetic methods based on the results: the survey content includes patients' comfort, satisfaction, and treatment effectiveness; Therapist: Conduct statistics on operability, learning curve, economy, and other aspects.

2 Statistical analysis

SPSS 23.0 software was used for data statistical analysis. The measurement data is represented by the mean \pm standard deviation, the inter group comparison is performed using one-way analysis of variance, the pairwise comparison between groups is performed using LSD test, the mean comparison between two samples is performed using t-test, and the rate comparison of categorical data is performed using chi square test. $P < 0.05$ indicates a statistically significant difference.

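### Does the two-group wording for allocation and masking leave the intelligent-versus-traditional device comparison unrandomised or unblinded?

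*Combined protocol and SAP*

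**What the plan says.** Section 1.1 gives the only allocation statement: "Divide patients into a control group and a treatment group using a random number table method". The sentence after it reads "There are 30 cases in the control group, 30 cases in the intelligent isokinetic treatment group, and 30 cases in the traditional isokinetic treatment group", within "A total of 90 stroke hemiplegic rehabilitation patients". No allocation ratio, restriction, list holder or concealment method is given.

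Section 1.2 opens with "Both the control group and the two treatment groups received conventional rehabilitation therapy". It later returns to the singular: "The control group received 110 minutes of daily training, while the observation group received 135 minutes of daily training". It also says "Traditional isokinetic therapy has the same treatment parameters as the intelligent isokinetic group in this project group".

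Section 1.3 says that, at both assessment times, "a dedicated person is assigned to assess whether the patient is in the control group or treatment group, which is a third-party blind assessment". The outcomes include rater-scored scales (Fugl-Meyer, muscle tone) and peak torque measured by an instrument. A questionnaire compares the two isokinetic methods.

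Section 2 plans one-way analysis of variance with LSD pairwise comparisons.

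**The concern.** The plan compares three arms, but its randomisation sentence names two. Taken at its word, the random number table separates control patients from treated patients, and nothing says how a treated patient came to receive one device rather than the other. That comparison is planned, and the intelligent device belongs to the project team, so an unprotected choice of device would open the way to selection bias.

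The exact 30/30/30 split adds to the doubt. Independent draws rarely produce it, so some restriction must have been used. If arms were simply closed on reaching 30, the last assignments could be foreseen.

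The masking sentence, taken literally, gives the assessor the task of determining the patient's group, which is the reverse of blinding. Patients and therapists can see which device is used, so the assessor is the main protection for the rater-scored outcomes.

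**Working it through.** **Inputs.** Total 90 and arms 30/30/30 (section 1.1). Session lengths 40, 30, 20 and 20 minutes for conventional therapy and 25 minutes for isokinetic training (section 1.2). The plan gives no figure for predictability or assessor bias.

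**The plan's own figures.** 30 + 30 + 30 = 90, as stated. Conventional therapy is 40 + 30 + 20 + 20 = 110 minutes, and 110 + 25 = 135 minutes, as stated.

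The second sum also helps with the wording. Section 1.2 gives 135 minutes to a single observation group, yet both isokinetic arms have the same treatment parameters, so the figure applies to both. The document thus uses a singular noun for the two active arms together. The same reading fits the randomisation sentence in section 1.1.

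**Is 30/30/30 surprising?** It depends on how the random number table is used.

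- Independent 1:1:1 draws: P(30/30/30) = 90! / [(30!)³ × 3⁹⁰] = 0.0091.
- Independent 1:1 draws, treatment against control: P(30 or fewer controls) = Σ C(90,k)/2⁹⁰ for k = 0 to 30, which is 0.0010.
- Ordering 90 patients by random numbers and cutting after 30 and 60: probability 1.

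The small probabilities exclude unrestricted draws. They say nothing against the third use, which also fits the plan's description.

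**How many final assignments could be foreseen?** Count the patients at the end for whom only one arm is open (forced), and those for whom two are open.

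- Random ordering of 30/30/30. The last k patients all come from one given arm with probability C(30,k)/C(90,k), and summing over k ≥ 1 gives 30/61. Mean forced = 3 × 30/61 = 1.48. The last k patients all avoid one given arm with probability C(60,k)/C(90,k), which sums to 60/31. Mean length with at most two arms open = 3 × (60/31 − 30/61) = 4.33. Mean with exactly two open = 4.33 − 1.48 = 2.86. In simulation the 5th to 95th percentile for forced patients is 1 to 3.
- Independent draws, closing each arm at 30 (simulation). Mean forced 4.9, 5th to 95th percentile 1 to 11, and a further 8.7 with two arms open.

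The forced share is therefore 1.48/90 = 1.6% or 4.9/90 = 5.4%. Either matters only if the enrolling person kept count and the list was not concealed. The plan is silent on both.

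**Would blocking improve this?** Take ten blocks of 3 and ten of 6, which is 30 + 60 = 90 patients. A block of 3 has one forced place. A block of 6 has on average 3 × 2/5 = 1.2. The total is 10 × 1 + 10 × 1.2 = 22 forced assignments if block boundaries become known. By this measure small blocks are worse, and any protection would come from concealment.

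**Masking.** The sentence in section 1.3 has two halves. The first, read alone, makes group membership the object of assessment. The second calls the procedure a blind assessment by a third party. Only one reading satisfies both: a dedicated outside person assesses patients of every group without being told the group. The literal reading contradicts the sentence's own ending, which is what a translation fault looks like.

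**The case for a change.** The strongest case for a change is that the reader cannot tell from the text what was done. No sentence says that the choice of device was randomised. Concealment is not mentioned, and the team has an interest in its own device. Corrected wording would cost almost nothing, and a probable translation fault is still a fault.

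Part of this stands. Sequence generation, restriction and concealment are unstated for all three groups, and a report of the trial should describe them as they were carried out. The documents cannot exclude a non-random device split. If there was one, intelligent versus traditional would be a non-randomised comparison.

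It does not go further. An absent detail is not evidence of a non-random split, and the three-arm sentence directly follows the randomisation sentence. Peak torque is measured by an instrument, so not every outcome depends on the rater. Section 1.1 also describes the patients admitted from January 2022 to January 2023 as already selected. If allocation is complete, a new list or envelope procedure cannot be introduced, and writing one into the plan would claim something the documents do not support.

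**Conclusion.** The wording is loose, but the design it describes can be recovered: three arms of 30 allocated by random number table, with outcomes assessed by a masked third party. The gap is one of procedural detail that an analyst or trial team would fill in the ordinary way, together with a clerical fault in the masking sentence. Neither alters the planned comparisons, so no change to the plan follows.

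The 0.9% probability is correct but applies only to independent draws. The mean number of forced final assignments is about 1.5 under one plausible scheme and 4.9 under another, out of 90, and is harmless if the list was concealed. The size of any assessor bias cannot be computed from the documents.

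This conclusion assumes that treatment group is a collective term for both isokinetic arms, and that the blind label in section 1.3 states the intention. If the device was in fact chosen other than at random, it would not hold for the intelligent-versus-traditional comparison.

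### Neither the allocation nor the unadjusted ANOVA takes account of baseline severity or time since onset, which costs precision and leaves any chance imbalance between arms of 30 unresolved

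*Combined protocol and SAP*

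**What the plan says.** Section 1.1 (General information) enrols "A total of 90 stroke hemiplegic rehabilitation patients". The entry range is wide in three respects:

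- **Stroke type:** patients qualify by "meeting the diagnostic criteria for cerebral infarction and cerebral hemorrhage", and no proportions are given.
- **Time since onset:** first-ever stroke with a course of one month or less, and no stated minimum.
- **Severity:** "and the lower limb of the hemiplegic side is classified as stage III or above", with no upper limit and no named staging scale.

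Allocation is covered by one sentence: "Divide patients into a control group and a treatment group using a random number table method". That sentence mentions two groups, and the next gives three: "There are 30 cases in the control group, 30 cases in the intelligent isokinetic treatment group, and 30 cases in the traditional isokinetic treatment group". No stratification, blocking or minimisation is described.

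Section 1.3 (Evaluation method) provides for baseline data: "Before and after treatment, a dedicated person is assigned to assess". Section 2 (Statistical analysis) states that "the inter group comparison is performed using one-way analysis of variance", with LSD for pairwise comparisons and t-tests for two-sample means. It names no covariate, no change-from-baseline model and no plan for handling imbalance.

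**The concern.** The entry criteria let through patients who may differ considerably in starting level and in days since stroke. Either the design (stratified allocation) or the analysis (covariate adjustment) could take account of this. As written, neither does.

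Two things are at stake. First, variation between patients that baseline data could explain stays in the error term, so each comparison is less precise than the same 90 patients allow. Second, if the arms do differ at entry, the plan gives no adjusted estimate, and a reader cannot tell how much of an observed difference reflects who was in each arm. The intelligent-versus-traditional comparison is the most exposed. Section 1.2 gives both arms the same treatment parameters, so any true difference between them may be small.

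**Working it through.** The documents contain no power calculation, effect size or SD. The only design figure is 3 × 30 = 90, which adds up. Everything below uses arms of 30 from section 1.1. Prevalences, onset distributions and correlations are assumptions.

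**1. Binary entry factor.** Split 90 patients at random into 30/30/30 and count how often arms differ by at least 6 of 30 patients (20 percentage points).

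| Assumed prevalence | Some pair of arms | Intelligent vs traditional |
|---|---|---|
| 20% | 17% | 8% |
| 30% | 26% | 12% |
| 40% | 31% | 15% |
| 50% | 33% | 16% |

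**2. Days since onset.** Assume a uniform distribution from the earliest entry day to day 31, and count how often some pair of arms differs by 4 days or more in mean onset time.

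| Earliest entry day | SD = (31 − earliest day)/√12 | Some pair differs by ≥ 4 days |
|---|---|---|
| 1 | 8.66 days | 17% |
| 7 | 6.93 days | 6% |
| 10 | 6.06 days | 3% |
| 14 | 4.91 days | 0.4% |

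The result depends heavily on when patients actually enter, which the documents do not say.

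**3. What an imbalance does to the outcome.** Shift in the unadjusted arm difference = gap in the factor × strength of its relation to outcome.

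- A 20-point gap on a factor worth an assumed 0.5 SD: 0.20 × 0.5 = 0.10 SD.
- A 4-day gap when entry starts at day 1 is 4/8.66 = 0.46 SD. At an assumed correlation of 0.3 to 0.5 the shift is 0.14 to 0.23 SD.
- A 0.5 SD gap on a factor correlated 0.5 to 0.7 with outcome: 0.25 to 0.35 SD. Such a gap arises in some pair in about 13% of trials and in one given pair in about 5%.

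For comparison, the standard error of an unadjusted pairwise difference is √(2/30) = 0.258 SD. The difference detectable with 80% power at two-sided 0.05 is 2.80 × 0.258 = 0.72 SD. Typical shifts are therefore below one standard error.

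**4. What adjustment gains.** With covariates jointly correlated ρ with the outcome, the standard error is multiplied by √(1 − ρ²).

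- ρ = 0.5: 0.258 × √0.75 = 0.224 SD.
- ρ = 0.7: 0.258 × √0.51 = 0.184 SD.

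Estimating four covariate coefficients has a small cost. With 90 − 3 = 87 error degrees of freedom before covariates, the variance rises on average by (87 − 1)/(87 − 4 − 1) = 86/82 = 1.05, and the standard error by √1.05 = 1.024. This gives 0.229 and 0.189 SD, or about 0.23 and 0.19. The detectable difference falls from 0.72 SD to 2.80 × 0.229 = 0.64 SD or 2.80 × 0.189 = 0.53 SD.

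**The case against.** The strongest defence is that the trial randomises, and plain randomisation of 90 patients is legitimate. Chance imbalance is already in the ANOVA error term, and the P < 0.05 threshold allows for it. That stands. A reader might infer that the wide entry range biases the comparison or makes false positives more likely; under valid randomisation it does neither.

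A reader might also infer that spontaneous recovery in the first month could match the training effect over three weeks. The documents give no recovery rate and no training effect, so that claim has no support here. That stage, onset time and stroke type predict recovery is itself a clinical premise the plan does not state. The safest predictor is the outcome's own baseline value.

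Three further points have force. The imbalance figures look largest when counted over any of three pairs, and the onset figure is largest when entry begins on day 1. That is doubtful for stable patients on a rehabilitation ward, so the ranges above matter. The absence of stratification is read from silence in a very short document; the exact 30/30/30 split implies some restriction on totals, although that does not balance prognosis. Finally, section 1.1 is in the past tense with a January 2022 to January 2023 window, so allocation may be finished.

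None of this answers the loss of precision, which adjustment can reduce even when allocation is complete.

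**Conclusion.** The point holds as one of precision and interpretability, and it is an inexpensive improvement rather than a flaw that invalidates the trial. Sizeable chance imbalance on a single binary factor is plausible (17% to 33% for some pair, 8% to 16% for the intelligent-versus-traditional pair). A 4-day onset gap ranges from 17% down to 0.4% depending on the earliest entry day. The effect on an outcome difference would usually be smaller than its standard error.

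The firmer gain is a reduction in pairwise standard error from about 0.26 SD to between 0.23 and 0.19 SD. It rests on an assumed joint correlation of 0.5 to 0.7 between the covariates and the outcome; a weaker correlation gives a smaller gain.

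**What to change.** **In section 2.** For continuous outcomes measured before and after treatment, replace the unadjusted one-way ANOVA, LSD and t-tests with ANCOVA of the post-treatment value on arm. Prespecify as covariates the outcome's baseline value, days since onset (continuous), lower-limb stage and stroke type. Take the pairwise contrasts from that model. Fix the covariate list before outcomes are examined by arm.

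The cost is a few degrees of freedom (about 2.4% on the standard error for four terms, as shown above). Stage, onset and stroke type are known from eligibility and the baseline values from the planned assessment, so no extra patients or visits are needed.

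**In section 1.1, only if allocation has not started.** Also stratify the list by lower-limb stage and time since onset, using concealed permuted blocks of varying size, with cut-offs set in advance by the trial team. Two binary stratifiers leave 90/4 = 22.5 patients per cell. Adding stroke type would leave 90/8 = 11.25, under 4 per arm per cell, so stroke type is better handled as a covariate. The downsides are slightly unequal arm sizes and some predictability of allocation in a single centre where therapists know the treatment, which varying block sizes and concealment reduce. If allocation is complete, the analysis change alone applies.

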1.2 Method

Both the control group and the two treatment groups received conventional rehabilitation therapy such as exercise therapy (once a day,

40 minutes a time, 5 times a week), occupational therapy (once a day, 30 minutes a time, 5 times a week), low-frequency electricity (once a day, 20 minutes a time, 5 times a week), acupuncture and moxibustion therapy (once a day, 20 minutes a time, 5 times a week), which complied with the recommendations on rehabilitation treatment in the 2017 edition of the Guidelines for Early Rehabilitation Treatment of Stroke in China; Intelligent isokinetic therapy adds isokinetic muscle strength training to the lower limb flexion and extension muscles of hemiplegia in the above treatments. The intelligent portable isokinetic tester of this project team was used for isokinetic training of the affected knee flexor and extensor muscles. The patient's seat backrest was adjusted to 85° , and the waist and shoulder cross straps were fixed. The proximal thighs of the test subjects were fixed with nylon buckles, the lateral condyle of the femur was the axis, and the length of the arm was 12 on the scale. The distal ankle of the lower leg was fixed above the ankle. Before training, passive joint movements were performed on the knee and ankle joints to avoid joint damage, And conduct three low resistance warm-up exercises. Choose $60^{\circ}/s$, $90^{\circ}/s$, and $120^{\circ}/s$ angular velocity isokinetic training based on the patient's specific situation. Train 10 times for each angular velocity, with 15 seconds of rest between each cycle, and 2 minutes of rest between each cycle. Train for 4 cycles according to the patient's tolerance, with an appropriate amount of training to cause

moderate muscle fatigue and no fatigue on the second day (a total of 25 minutes per training session). Train each muscle group once a day, 5 days a week, for a total of 3 weeks. The control group received 110 minutes of daily training, while the observation group received 135 minutes of daily training. Traditional isokinetic therapy has the same treatment parameters as the intelligent isokinetic group in this project group.

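### Do the two rest times given for the same interval in the isokinetic prescription require a change to the plan?

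*Combined protocol and SAP*

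**What the plan says.** Section 1.2 gives the added isokinetic training in a few sentences:

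- Joint preparation comes first: passive movement, then the instruction to "conduct three low resistance warm-up exercises".
- Speeds of 60, 90 and 120 degrees per second are available, with "angular velocity isokinetic training based on the patient's specific situation".
- The work per speed is "Train 10 times for each angular velocity".
- The rests are given as "with 15 seconds of rest between each cycle, and 2 minutes of rest between each cycle".
- The number of cycles is flexible: "Train for 4 cycles according to the patient's tolerance".
- The session length is fixed: "a total of 25 minutes per training session", 5 days a week for 3 weeks, with the instruction "Train each muscle group once a day".
- The second device arm follows the first: "Traditional isokinetic therapy has the same treatment parameters as the intelligent isokinetic group in this project group".

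The same section gives daily training time as 110 minutes for control and 135 minutes with isokinetic training. Neither Section 1.1 nor Section 1.3 says what a cycle is.

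**The concern.** Read literally, the rest between cycles is both 15 seconds and 2 minutes, and one interval cannot have both lengths. Because a cycle is undefined, it could be one set of ten at one speed or a full pass through the chosen speeds, and the wording does not say which rest belongs where.

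The sentence describes the only component added to conventional rehabilitation, so it governs the treatment of two of the three arms. If the work-to-rest pattern is unknown, another centre cannot reproduce the session exactly, and a reader cannot tell how much of the extra 25 minutes was exercise. If the ambiguity also reached a between-group comparison, it would affect the interpretation of the trial. That is what needs checking.

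**Working it through.** **Stated totals.** Conventional therapy is 40 + 30 + 20 + 20 = 110 minutes a day. Adding the isokinetic session gives 110 + 25 = 135 minutes. Both match Section 1.2, and neither depends on where the rests fall.

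**Can the 25 minutes identify the intended reading?** Inputs from Section 1.2 are rests of 15 s and 120 s, 10 repetitions per speed, 4 cycles and up to 3 speeds. Four full cycles are assumed throughout, although the section lets tolerance reduce them. The sums count rest only.

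*A cycle is a full pass through the speeds.* Three speeds give 2 × 4 = 8 gaps between speeds and 3 gaps between cycles. Two speeds give 4 and 3.

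| Speeds | 15 s between speeds, 120 s between cycles | 120 s between speeds, 15 s between cycles |
|---|---|---|
| 3 | 8×15 + 3×120 = 480 s = 8.0 min | 8×120 + 3×15 = 1005 s = 16.75 min |
| 2 | 4×15 + 3×120 = 420 s = 7.0 min | 4×120 + 3×15 = 525 s = 8.75 min |

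With one speed there is no gap between speeds. Only one of the two rests then has a place: 3×15 = 45 s (0.75 min) or 3×120 = 360 s (6.0 min).

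*A cycle is one set of ten, with four sets at each of three speeds.* There are 9 gaps between sets and 2 between speeds: 9×15 + 2×120 = 375 s (6.25 min), or swapped, 9×120 + 2×15 = 1110 s (18.5 min).

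*15 s between single repetitions, 120 s between cycles.* Each set of ten has 9 gaps.
- Three speeds: 12×9×15 + 3×120 = 1980 s (33.0 min), which exceeds 25.
- Two speeds: 8×9×15 + 3×120 = 1440 s (24.0 min), leaving 1.0 min for everything else.
- One speed: 4×9×15 + 3×120 = 900 s (15.0 min).

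*Flexors and extensors trained in separate blocks.* The full-pass totals double to 16.0 and 33.5 min with three speeds, and to 14.0 and 17.5 min with two. Only 33.5 exceeds 25.

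**Adding exercise time.** The movement arc is not given. Assume 60 to 120 degrees, flexion plus extension in each repetition, and all three speeds. One pass takes 10×2×arc×(1/60 + 1/90 + 1/120), which is 43.3 to 86.7 s, so four passes take 2.9 to 5.8 min. The two full-pass, three-speed readings become 8.0 + 2.9 = 10.9 to 8.0 + 5.8 = 13.8 min, and 16.75 + 2.9 = 19.6 (rounded down) to 16.75 + 5.8 = 22.5 min (rounded down). Both leave room for passive movement and warm-up, whose times are not given. The total rules out some readings but leaves several.

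**Does the ambiguity reach a comparison?**
- *Intelligent versus traditional device:* the same parameters are stated for both arms, so any reading applies to 30 + 30 = 60 patients alike and drops out of the contrast.
- *Device versus control:* the contrast is conventional care with or without a 25-minute session. That description holds under every reading.
- *Analysis:* Section 2 uses one-way analysis of variance, LSD comparisons, t-tests and chi-square tests on outcome data. None takes rest time or cycle structure as an input.

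**The case for a change.** The strongest case for acting is that the contradiction can be verified, the repair is one sentence, and context does not remove the doubt. The tempting reading (short rest between speeds, long rest between cycles) needs more than one speed per session. Yet speeds are chosen patient by patient, and Section 1.3 says most subjects struggle with faster movement. For a patient training at one speed, that reading leaves one of the rests without a place. It could also be said that shared wording does not guarantee shared practice: staff on the two devices might have read the same sentence differently.

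The first part stands. The text is unclear, more than one reading survives, and exact replication suffers. The second part is possible in principle, but nothing in the document suggests it. The document states equal parameters, and a departure from that would be a matter of how the treatment was delivered. It would not be a fault in the plan.

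Three things limit the weight of the point. Two rests joined in one list suggest two different intervals with a noun repeated by mistake, as happens in translation, although the document does not confirm it. The prescription is in any case individually adjusted, by tolerance and by a fatigue target, so rest placement is one detail among several that vary by patient. And 60 of 90 is the number of patients the sentence covers; it does not measure an effect.

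**Conclusion.** The wording is ambiguous, but no change to the plan follows. The rest times and the undefined cycle must be reconciled when the training is described, by the investigators and from what was actually done; no view is taken here on which rest applies where. That is a drafting clarification with no gain for inference. The session length, frequency, duration and daily totals are stated independently of it, both device arms share it, and no planned test depends on it.

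In size, the unresolved part is the split of a fixed 25 minutes between rest and work. With four full cycles, three speeds and both muscle groups worked together, rest ranges from 6.25 to 18.5 minutes across the full-pass and set-based readings calculated. Fewer speeds, fewer cycles or separate muscle-group blocks would move these figures, so they illustrate the spread and are not limits. The conclusion rests on the stated equality of parameters between the device arms. No effect on any outcome, on sample size or on any between-group comparison has been shown.
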